### **5.1.3 Subject Exclusion Criteria**

The subject must be excluded from participating in the trial if the subject:

1. Has received prior therapy with an anti-PD-1, anti-PD-L1, anti-PD-L2, anti-CD137, or anti-Cytotoxic T-lymphocyte-associated antigen-4 (CTLA-4) agents (including ipilimumab or any other antibody/drug specifically targeting T-cell co-stimulation or checkpoint pathways).
2. Is currently participating or has participated in a study with an investigational compound or device within 30 days, or 5X half-life of the investigational compound, whichever is longer, of initial dosing on this study.
3. Has had chemotherapy, targeted small molecule therapy, radiotherapy, or biological cancer therapy (including monoclonal antibodies) within 4 weeks prior to the first dose of trial treatment, or who has not recovered ( $\leq$  Grade 1 or baseline) from adverse events due to a previously administered agent.

Note: Subjects with  $\leq$  Grade 2 neuropathy or alopecia are an exception to this criterion and may qualify for the study.

Note: If subject received major surgery or radiation therapy of  $> 30$  Gy, they must have recovered from the toxicity and/or complications from the intervention prior to starting therapy.

4. Has a known history of another (including unknown primary) malignancy within 5 years prior to first study drug administration.

Note: Exceptions include adequately treated Stage 1 or Stage 2 basal/squamous cell carcinoma of the skin, superficial bladder cancer, or cancer in situ which has undergone potentially curative therapy, or no evidence of that disease recurrence for 5 years since initiation of that therapy.

5. Is expected to require any other form of systemic or localized antineoplastic therapy while in study.

6. Has known active central nervous system (CNS) mets and/or carcinomatous meningitis.

Note: Subjects with previously treated brain metastases and clinically stable CNS mets are allowed to participate (clinically stable is defined as a period (at least 4 weeks prior to the first dose of trial treatment) in which (1) there is no evidence of new or enlarging CNS mets by MRI, (2) the subject is off steroids for at least two weeks, and (3) any neurologic symptoms have returned to baseline).

7. Has an active autoimmune disease requiring systemic treatment within the past 3 months prior to first study drug administration, a documented history of clinically severe autoimmune disease, or a syndrome that requires systemic steroids or immunosuppressive agents.

Note: Subjects with vitiligo, diabetes mellitus type I, or resolved childhood asthma/atopy would be an exception to this rule. Subjects that require intermittent use of bronchodilators or local steroid injections would not be excluded from the study. Subjects with hypothyroidism stable on hormone replacement or Sjorgen's syndrome will not be excluded from the study.

8. Is receiving systemic steroid therapy or any other form of immunosuppressive therapy within 1 week prior to the first dose of trial treatment.
9. Has an active infection requiring intravenous systemic therapy.
10. Has received a live vaccine within 4 weeks prior to the first dose of trial treatment (refer to Section 5.5.2 for further details).
11. Has a known hypersensitivity to the components of the study drug or another monoclonal antibody.
12. Has history or evidence of active pneumonitis.
13. Is known to be Human Immunodeficiency Virus (HIV)-positive (HIV 1/2 antibodies).
14. Has known history of active Hepatitis B (HBsAg reactive) or C (HCV RNA [qualitative] is detected).
15. Has a history or current evidence of any condition, therapy, or lab abnormality that might confound the results of the study, interfere with the subject's participation for the full duration of the study, or is not in the best interest of the subject to participate.
16. Has known psychiatric or substance abuse disorders that would interfere with cooperation with the requirements of the trial.

17. Is pregnant or breastfeeding, or expecting to conceive or father children within the projected duration of the trial, starting with the screening visit (Visit 1) through 120 days after the last dose of trial treatment.
18. Is or has an immediate family member (e.g., spouse, parent/legal guardian, sibling or child) who is investigational site or sponsor staff directly involved with this trial unless, prospective IRB approval (by chair or designee) is given allowing exception to this criterion for a specific subject.

## **5.2 Trial Treatment(s)**

The treatment to be used in this trial is outlined below in [Table 2](#).

Table 2 Trial Treatment

Drug	Dose/Potency	Dose Frequency	Route of Administration	Regimen/Treatment	Use
MK-3475	2 mg/kg	Q3W	IV infusion	Day 1 of each cycle	Experimental

The MK-3475 dosing interval may be increased due to toxicity as described in Section 5.2.1.2.

Trial treatment should begin on the day of randomization or as close as possible to the date on which the subject is allocated/assigned.

The investigator shall take responsibility for and shall take all steps to maintain appropriate records and ensure appropriate supply, storage, handling, distribution and usage of trial treatments in accordance with the protocol and any applicable laws and regulations.

### **5.2.1 Dose Selection/Modification**

#### **5.2.1.1 Dose Selection (Preparation)**

The rationale for selection of doses to be used in this trial is provided in Section 4.0 – Background and Rationale. The dose amount required to prepare the MK-3475 infusion solution will be based on the subject's weight in kilograms (kg). Details on the dose calculation, preparation and administration are provided in the Procedures Manual.

#### **5.2.1.2 Dose Modification (Escalation/Titration/Other)**

Adverse events (both non-serious and serious) associated with pembrolizumab exposure may represent an immunologic etiology. These adverse events may occur shortly after the first dose or several months after the last dose of treatment. Pembrolizumab must be withheld for drug-related toxicities and severe or life-threatening AEs as per [Table 3](#) below. See Section 5.6 for supportive care guidelines, including use of corticosteroids.

Table 3 Dose Modification Guideline

Toxicity	Hold Treatment For Grade	Timing for Restarting Treatment	Treatment Discontinuation
Diarrhea/Colitis	2-3	Toxicity resolves to Grade 0-1	Toxicity does not resolve within 12 weeks of last dose or inability to reduce corticosteroid to 10 mg or less of prednisone or equivalent per day within 12 weeks
	4	Permanently discontinue	Permanently discontinue
AST, ALT, or Increased Bilirubin	2	Toxicity resolves to Grade 0-1	Toxicity does not resolve within 12 weeks of last dose or inability to reduce corticosteroid to 10 mg or less of prednisone or equivalent per day within 12 weeks
	3-4	Permanently discontinue (see exception below) a	Permanently discontinue
Type 1 diabetes mellitus (if new onset) or Hyperglycemia	T1DM or 3-4	Hold pembrolizumab for new onset Type 1 diabetes mellitus or Grade 3-4 hyperglycemia associated with evidence of beta cell failure	Resume pembrolizumab when patients are clinically and metabolically stable
Hypophysitis	2-4	Toxicity resolves to Grade 0-1. Therapy with pembrolizumab can be continued while endocrine replacement therapy is instituted	Toxicity does not resolve within 12 weeks of last dose or inability to reduce corticosteroid to 10 mg or less of prednisone or equivalent per day within 12 weeks
Hyperthyroidism	3	Toxicity resolves to Grade 0-1	Toxicity does not resolve within 12 weeks of last dose or inability to reduce corticosteroid to 10 mg or less of prednisone or equivalent per day within 12 weeks
	4	Permanently discontinue	Permanently discontinue
Hypothyroidism		Therapy with pembrolizumab can be continued while thyroid replacement therapy is instituted	Therapy with pembrolizumab can be continued while thyroid replacement therapy is instituted
Infusion Reaction	2 b	Toxicity resolves to Grade 0-1	Permanently discontinue if toxicity develops despite adequate premedication
	3-4	Permanently discontinue	Permanently discontinue
Pneumonitis	2	Toxicity resolves to Grade 0-1	Toxicity does not resolve within 12 weeks of last dose or inability to reduce corticosteroid to 10 mg or less of prednisone or equivalent per day within 12 weeks
	3-4	Permanently discontinue	Permanently discontinue
Renal Failure or Nephritis	2	Toxicity resolves to Grade 0-1	Toxicity does not resolve within 12 weeks of last dose or inability to reduce corticosteroid to 10 mg or less of prednisone or equivalent per day within 12 weeks
	3-4	Permanently discontinue	Permanently discontinue
All Other Drug-Related Toxicity c	3 or Severe	Toxicity resolves to Grade 0-1	Toxicity does not resolve within 12 weeks of last dose or inability to reduce corticosteroid to 10 mg or less of prednisone or equivalent per day within 12 weeks
	4	Permanently discontinue	Permanently discontinue

Note: Permanently discontinue for any severe or Grade 3 (Grade 2 for pneumonitis) drug-related AE that recurs, or any life-threatening event.

a For patients with liver metastasis who begin treatment with Grade 2 AST or ALT, if AST or ALT increases by greater than or equal to 50% relative to baseline and lasts for at least 1 week then patients should be discontinued.

b If symptoms resolve within one hour of stopping drug infusion, the infusion may be restarted at 50% of the original infusion rate (e.g., from 100 mL/hr to 50 mL/hr). Otherwise dosing will be held until symptoms resolve and the subject should be premedicated for the next scheduled dose; Refer to [Table 4](#) – Infusion Treatment Guidelines for further management details.

c Patients with intolerable or persistent Grade 2 drug-related AE may hold study medication at physician discretion. Permanently discontinue study drug for persistent Grade 2 adverse reactions for which treatment with study drug has been held, that do not recover to Grade 0-1 within 12 weeks of the last dose.

Dosing interruptions are permitted in the case of medical / surgical events or logistical reasons not related to study therapy (e.g., elective surgery, unrelated medical events, patient vacation, and/or holidays). Subjects should be placed back on study therapy within 3 weeks of the scheduled interruption, unless otherwise discussed with the Sponsor. The reason for interruption should be documented in the patient's study record.

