- For **Grade 3 or 4 diarrhea/colitis**, treat with intravenous steroids followed by high dose oral steroids.
- When symptoms improve to Grade 1 or less, steroid taper should be started and continued over no less than 4 weeks.
- **Type 1 diabetes mellitus (if new onset, including diabetic ketoacidosis [DKA]) or  $\geq$  Grade 3 Hyperglycemia, if associated with ketosis (ketonuria) or metabolic acidosis (DKA)**
  - For **T1DM** or **Grade 3-4** Hyperglycemia
    - Insulin replacement therapy is recommended for Type I diabetes mellitus and for Grade 3-4 hyperglycemia associated with metabolic acidosis or ketonuria.
    - Evaluate patients with serum glucose and a metabolic panel, urine ketones, glycosylated hemoglobin, and C-peptide.
- **Hypophysitis:**
  - For **Grade 2** events, treat with corticosteroids. When symptoms improve to Grade 1 or less, steroid taper should be started and continued over no less than 4 weeks. Replacement of appropriate hormones may be required as the steroid dose is tapered.
  - For **Grade 3-4** events, treat with an initial dose of IV corticosteroids followed by oral corticosteroids. When symptoms improve to Grade 1 or less, steroid taper should be started and continued over no less than 4 weeks. Replacement of appropriate hormones may be required as the steroid dose is tapered.
- **Hyperthyroidism or Hypothyroidism:**

Thyroid disorders can occur at any time during treatment. Monitor patients for changes in thyroid function (at the start of treatment, periodically during treatment, and as indicated based on clinical evaluation) and for clinical signs and symptoms of thyroid disorders.

  - **Grade 2** hyperthyroidism events (and **Grade 2-4** hypothyroidism):
    - In hyperthyroidism, non-selective beta-blockers (e.g. propranolol) are suggested as initial therapy.
    - In hypothyroidism, thyroid hormone replacement therapy, with levothyroxine or liothyroinine, is indicated per standard of care.

- **Grade 3-4** hyperthyroidism
  - Treat with an initial dose of IV corticosteroid followed by oral corticosteroids. When symptoms improve to Grade 1 or less, steroid taper should be started and continued over no less than 4 weeks. Replacement of appropriate hormones may be required as the steroid dose is tapered.
- **Hepatic:**
  - For **Grade 2** events, monitor liver function tests more frequently until returned to baseline values (consider weekly).
    - Treat with IV or oral corticosteroids

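### Table 3 tells sites both to resume and to stop for good after life-threatening new-onset diabetes or hyperglycemia; hypophysitis has a weaker form of the same problem

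*Combined protocol and SAP*

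**What the plan says.** All the dosing rules at issue are in Section 5.2.1.2.

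- **Opening paragraph:** "Pembrolizumab must be withheld for drug-related toxicities and severe or life-threatening AEs as per" Table 3. It speaks of withholding and says nothing about permanence.
- **T1DM/hyperglycemia row:** "Hold pembrolizumab for new onset Type 1 diabetes mellitus or Grade 3-4 hyperglycemia associated with evidence of beta cell failure". The last cell of the row then says "Resume pembrolizumab when patients are clinically and metabolically stable". No permanent stop appears anywhere in the row.
- **Hypophysitis row, Grade 2-4:** "Toxicity resolves to Grade 0-1. Therapy with pembrolizumab can be continued while endocrine replacement therapy is instituted". The row ends treatment only if the event has not resolved, or steroids cannot be tapered to the stated dose, within 12 weeks.
- **Note below the table:** "Permanently discontinue for any severe or Grade 3 (Grade 2 for pneumonitis) drug-related AE that recurs, or any life-threatening event".

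Section 5.6.1 (Supportive Care Guidelines) counts diabetic ketoacidosis as part of the new-onset T1DM event and adds: "Insulin replacement therapy is recommended for Type I diabetes mellitus and for Grade 3-4 hyperglycemia associated with metabolic acidosis or ketonuria". It sends the reader back to Section 5.2.1 for dosing. Section 5.8 makes unacceptable adverse experiences, as described in Section 5.2.1.2, a reason for mandatory discontinuation of treatment.

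**The concern.** A dose-modification table should give one answer for one event. Here, a subject who has life-threatening hyperglycemia or ketoacidosis and is then stabilised on insulin falls under an instruction to resume and an instruction to stop permanently. Two careful investigators could act in opposite ways, each citing Table 3. One choice re-exposes a patient whom the Note says must stop. The other ends therapy for a patient whom the row says should resume.

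The choice also decides whether the case counts as a mandatory treatment discontinuation under Section 5.8. Safety and tolerability are a primary objective (Section 3.1), so stopping rules for toxicity should be applied in the same way at every site.

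**Working it through.** The plan gives no figure to reproduce and no arithmetic applies beyond a count of rows. The check sets the provisions side by side.

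**1. What counts as life-threatening.** Table 7 (Section 7.2.4) offers two meanings. CTCAE Grade 4 is defined by life-threatening consequences. The seriousness criterion is narrower and requires immediate risk of death in the investigator's view. On the broad meaning, every Grade 4 event triggers the Note. On the narrow one, a Grade 4 event without immediate risk of death simply follows its row. Ketoacidosis with immediate risk of death meets both meanings, so the conflict does not depend on which is chosen.

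**2. Row against Note, by severity (first occurrence).**

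| Event | Row | Note |
|---|---|---|
| Grade 3 hyperglycemia with beta cell failure | Hold, then resume | Not triggered |
| Life-threatening T1DM/hyperglycemia | Hold, then resume | Permanent stop |
| Grade 2-3 hypophysitis | May restart or continue | Not triggered |
| Life-threatening hypophysitis | May restart or continue | Permanent stop |

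The second line sets one instruction against another, so both cannot be followed. The fourth sets a permission against a prohibition. A site can comply with both by not using the permission, so that problem is weaker.

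**3. Count of rows at Grade 4.** Permanent stop stated: diarrhea/colitis, liver tests (with a footnoted exception), hyperthyroidism, infusion reaction, pneumonitis, renal, all other drug-related toxicity = 7. Instruction to resume: T1DM/hyperglycemia = 1. Permission to restart or continue: hypophysitis = 1. No grade stated: hypothyroidism = 1. Total 7 + 1 + 1 + 1 = 10.

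**4. Search for a rule of precedence.**

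- Footnotes a to c to Table 3 deal with liver tests, infusion reactions and other toxicity. None exempts the T1DM/hyperglycemia or hypophysitis row.
- Section 5.8 refers back to Section 5.2.1.2.
- Table 7 requires advance approval by the Sponsor Clinical Director for rechallenge after a serious, possibly drug-caused event. That approval is to follow the protocol's dose-modification guidelines, which means this table again.
- Section 7.1.1.9 brings in the sponsor only for toxicity interruptions longer than 12 weeks.

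None of these says whether a row or the Note prevails.

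**The case against.** **The specific row governs the general Note.** This is the best argument. Seven rows list Grade 4, or Grade 3-4, as a permanent stop. The two disputed rows name Grade 4 and treat it differently, and Section 5.6.1 plans insulin or hormone replacement at Grade 3-4. That makes the rows look deliberate, and it is a fair guide to the likely intent. But the table also points the other way. The Note's recurrence clause is meant to override rows: it stops a recurrent Grade 3 diarrhea that the row alone would let restart. Nor can an unwritten endocrine exemption be inferred, because Grade 4 hyperthyroidism is a permanent stop. The intent is plausible but not stated.

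**Ketoacidosis could be handled as its own event.** Table 3 does not name it, so a site might use the row for all other drug-related toxicity, where Grade 4 is a permanent stop. That is arguable. However, Section 5.6.1 places ketoacidosis within the T1DM event, and life-threatening hyperglycemia with beta cell failure would remain in its own row either way.

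**Safeguards exist.** A life-threatening adverse event is serious and reaches the sponsor within 24 hours (Section 7.2.3.1). Rechallenge needs sponsor approval when the event is serious and possibly drug-caused (Table 7). A committee evaluates safety information (Section 7.3.1). This stands as mitigation: a reader might infer that sites would re-dose such patients on the table alone, and the documents do not support that. But the safeguards supply no rule, and the approver is referred to the same conflicting table.

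**A separate guidance document on events of clinical interest may settle it.** Section 7.2.3.2 says it covers management of these events. It was not available, and the protocol does not say that it overrides Table 3.

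**Conclusion.** The inconsistency is real and narrow. It is a direct contradiction in one row of ten (T1DM/hyperglycemia) at life-threatening severity, and a permission that the Note would withdraw in a second (hypophysitis). First-occurrence Grade 2-3 events are not affected.

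Three stronger readings are tempting, and the documents do not support them:

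- *That hypophysitis is as direct a conflict, and that hypothyroidism is another.* The hypophysitis text permits and does not instruct. The hypothyroidism row, "Therapy with pembrolizumab can be continued while thyroid replacement therapy is instituted", names no grade. That is missing detail, not a contradiction.
- *That the conflict specifically costs subjects the Second Course Phase.* Any stop before 24 months outside the confirmed-complete-response route has that effect (Section 7.1.5.2.1).
- *That the efficacy result is in doubt.* The exact binomial test of response rate does not depend on which reading is taken.

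The documents give no rate for these events and the trial enrols about 35 subjects, so the expected number of cases cannot be stated. The hyperglycemia trigger also requires evidence of beta cell failure, which narrows it further. The conclusion rests on the protocol text alone and assumes that no document outside it sets the precedence. The matter is worth correcting because it concerns a stopping rule for life-threatening toxicity and costs very little to settle.

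**What to change.** Add one exception to the Note, attached only to its life-threatening clause, for example: *except new-onset T1DM/hyperglycemia and hypophysitis controlled on insulin or hormone replacement, which follow their rows (rechallenge after a serious, possibly drug-related event needs Sponsor Clinical Director approval as in Table 7)*. The recurrence clause stays as it is. The bracketed reminder restates an existing requirement and adds no new one.

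This direction fits the rows and Section 5.6.1, but it relaxes an unqualified stop rule, so the clinical choice is the sponsor's. If the Note is meant to prevail, split Grade 4 out of the T1DM/hyperglycemia and hypophysitis rows as a permanent discontinuation.

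Either way the cost is one clause or two table lines, with no added visits, tests or data. No edit to the hypothyroidism row is needed, and no new approval step where a dose was never held.

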AST (SGOT) and ALT (SGPT)	$\leq 2.5 \times$ ULN OR $\leq 5 \times$ ULN for subjects with liver metastases
Endocrine	
Thyroid stimulating hormone (TSH)	Within normal range
Coagulation	
Prothrombin Time (PT) / International Normalized Ratio (INR), activated Partial Thromboplastin Time (aPTT)	$\leq 1.5 \times$ ULN unless the subject is receiving anticoagulant therapy as long as PT or aPTT is within therapeutic range of intended use of anticoagulants

a Creatinine clearance should be calculated per institutional standard. If no local guideline is available, Creatinine Clearance should be calculated using the Cockcroft-Gault Method:  
 $\text{CrCl} = [(140-\text{age}) * \text{weight (kg)} * (0.85 \text{ for females only})] / (72 * \text{serum creatinine})$

8. Have provided tissue for PD-L1 expression evaluation from an archival tissue sample or newly obtained core or excisional biopsy of a tumor lesion not previously irradiated.

Note: Subjects will be eligible to participate regardless of the level of PD-L1 expression.

9. Have documented BRAF mutation status or be willing to provide a tumor tissue for BRAF genotyping.

Note: BRAF V600 mutation analysis should be performed at screening in subjects without documented BRAF status.

10. (Female subject of childbearing potential) Have a negative urine or serum pregnancy test within 72 hours prior to receiving the first dose of study medication. If the urine test is positive or borderline a serum pregnancy test will be required.

11. (Female subjects of childbearing potential) Be willing to use 2 methods of birth control or be surgically sterile, or abstain from heterosexual activity for the course of the study through 120 days after the last dose of study medication (Refer to Section 5.7.2). The commonly used criteria for subjects of child bearing potential are those who have not been surgically sterilized or have not been free from menses for >1 year.
12. (Male subjects) Agree to use an adequate method of contraception starting with the first dose of study therapy through 120 days after the last dose of study therapy.

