### **7.1.5.4 Post-Treatment Visits**

#### **7.1.5.4.1 Safety Follow-Up Visit**

The mandatory Safety Follow-Up Visit should be conducted approximately 30 days after the last dose of trial treatment or before the initiation of a new anti-neoplastic treatment, whichever comes first. All AEs that occur prior to the Safety Follow-Up Visit should be recorded. Subjects with an AE of Grade > 1 will be followed until the resolution of the AE to Grade 0-1 or baseline until the beginning of a new anti-neoplastic therapy, whichever occurs first. SAEs that occur within 90 days of the end of treatment or 30 days of the end of treatment if the subject initiates new anticancer therapy, whichever is earlier, should also be followed and recorded.

Subjects who are eligible for retreatment with MK-3475 (as described in Section 7.1.5.2.1) may have up to two safety follow-up visits, one after the Treatment Period and one after the Second Course Phase.

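### For subjects with liver metastases who start at Grade 2 AST/ALT, Table 3 can require recovery below the entry grade, and footnote a does not say which lines it changes

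*Combined protocol and SAP*

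**What the plan says.** **Entry.** Section 5.1.2, Table 1 limits AST and ALT to 2.5×ULN, with a higher limit of 5×ULN: "ULN for subjects with liver metastases".

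**Grade 2 line.** In Section 5.2.1.2, the Table 3 row "AST, ALT, or Increased Bilirubin" has two lines. On the Grade 2 line treatment is held, and the restart condition is "Toxicity resolves to Grade 0-1". The discontinuation condition is "Toxicity does not resolve within 12 weeks of last dose", or failure to reduce corticosteroid to the stated level in the same period. The line carries no footnote mark and no alternative of return to baseline.

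**Grade 3-4 line.** The hold column lists Grades 3-4. The restart column reads "Permanently discontinue (see exception below", with the mark for footnote a. The last column orders permanent discontinuation again, this time with no mark.

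**Footnote a.** It applies "For patients with liver metastasis who begin treatment with Grade 2 AST or ALT". Such a subject is to be discontinued if AST or ALT rises by 50% or more over baseline for at least 1 week.

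**Elsewhere.** For Grade 2 hepatic events, Section 5.6.1 asks for closer liver-test monitoring until values are back at baseline, and starts the steroid taper at Grade 1 or less. Section 7.1.5.4.1 has adverse events above Grade 1 "followed until the resolution of the AE to Grade 0-1 or baseline". Section 5.8 makes unacceptable adverse experiences, as described in Section 5.2.1.2, a reason for mandatory treatment discontinuation.

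**The concern.** Eligibility deliberately admits a group whose starting AST/ALT may already be Grade 2. For a drug-related Grade 2 event in that group, the Grade 2 line sets a recovery target below the value at which the subject was accepted. That target may be out of reach for reasons unrelated to the drug, and missing it within 12 weeks means permanent discontinuation.

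The footnote written for this group uses a different yardstick, change from baseline, and is attached to a different line. A site therefore has two stated rules for the same subject and no statement of which governs. Depending on the line applied, the subject may be held, stopped or continued. In a single-arm trial of about 35 subjects, exposure, the reported reason for discontinuation and the opportunity to respond could then vary by site reading. Second Course entry reuses the Section 5.1.2 organ-function limits (Section 7.1.5.2.1), so the conflict can recur there.

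**Working it through.** There is no plan figure to reproduce. The check sets the lines side by side and locates where they disagree.

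**Inputs from the protocol**
- Entry limit with liver metastases: 5×ULN (Table 1).
- Footnote a trigger: 1.5 × baseline B, sustained for at least 1 week.
- Grade 2 line: restart at Grade 0-1; discontinue if not resolved by 12 weeks.

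**Assumption.** The protocol grades by CTCAE version 4.0 but does not print the AST/ALT cut-offs. I take Grade 2 as above 3 to 5×ULN and Grade 3 as starting above 5×ULN, and vary both limits below.

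**1. Fall needed to restart under the Grade 2 line**

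Required fall from entry = 1 − (lower limit of Grade 2) / B.

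| B (×ULN) | Lower limit 3.0 | Lower limit 2.5 |
|---|---|---|
| 3.5 | 14.3% | 28.6% |
| 4.0 | 25.0% | 37.5% |
| 5.0 | 40.0% | 50.0% |

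**2. A smaller rise held, a larger one below the footnote's trigger**

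With Grade 3 starting above g, a value can be Grade 3 yet short of a 50% rise only if 1.5B > g, that is B > g/1.5. At g = 5, B must exceed 5/1.5 = 3.33×ULN.

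Example at B = 4.0, where the trigger is 1.5 × 4.0 = 6.0×ULN:
- 4.8×ULN is +20% and Grade 2: hold, restart only at 3.0×ULN or less.
- 5.9×ULN is +47.5% and Grade 3: the footnote's condition for discontinuation is not met.

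| g (×ULN) | B above which this can occur (g/1.5) |
|---|---|
| 4.5 | 3.00 |
| 5.0 | 3.33 |
| 5.5 | 3.67 |
| 6.0 | 4.00 |

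Every cut-off lies within the entry limit of 5×ULN. A Grade 3 rise of 50% or more that lasts under 1 week also misses the trigger.

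**3. The opposite conflict at lower baselines**

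If B is below g/1.5, a 50% rise stays within Grade 2. At B = 3.1, 1.5 × 3.1 = 4.65×ULN, which is Grade 2 when g = 5. If sustained for a week, footnote a says discontinue while the Grade 2 line says hold. With a lower Grade 2 limit of 3.0, this form needs B between 3.0 and g/1.5: from 3.0 to 3.33 at g = 5, from 3.0 to 4.0 at g = 6, and nowhere at g = 4.5.

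**4. What happens in the exempt Grade 3 case**

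The exception is marked in the restart column only. The hold column still lists Grades 3-4 and the last column still orders permanent discontinuation. The table does not say whether the subject in step 2 at 5.9×ULN continues, is held, or is stopped.

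**The case against.** **Scope of Table 3.** Its lead-in covers drug-related toxicities and severe or life-threatening events. Section 7.2 makes the worsening of an existing condition the adverse event, and Section 5.6.1 ties its guidance to events judged related. A reader might infer that every subject with liver metastases, or everyone entering at Grade 2, is held for the entry value itself. The documents do not support that. The conflict needs Grade 2 at entry and then a drug-related AST/ALT event.

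**The inversion.** A reader might also infer that Table 3 generally treats smaller rises more strictly than larger ones. It does not. A rise of 50% or more lasting a week means discontinuation under footnote a, which is stricter than a hold. The inversion needs a rise under 50%, or one lasting under a week, that crosses into Grade 3. It also needs footnote a to override the whole Grade 3-4 line, which the unmarked last column leaves open.

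**Reading footnote a as the rule for the whole group.** Its words are not confined to Grade 3-4, so it could be taken to govern everyone who starts at Grade 2. That would remove the inversion, but the mark sits on one line only and the Grade 2 line keeps its own terms.

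**Other routes.** Section 7.1.1.9 sends toxicity interruptions over 12 weeks to documented consultation with the sponsor, and a separate guidance document on events of clinical interest, not available here, may say more. Neither changes what Table 3 states, and Section 5.8 makes Section 5.2.1.2 binding. It is fair to add that the return-to-baseline wording in Section 5.6.1 concerns monitoring, and that in Section 7.1.5.4.1 the length of adverse-event follow-up. They show a different recovery standard in use, not a competing restart rule.

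**Bilirubin.** Table 1 admits some subjects with raised total bilirubin, and footnote a names only AST and ALT, so a reader might extend the point. The protocol prints no bilirubin grade cut-offs, and a stable raised value is not by itself a drug-related increase. The extension is not established.

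**Conclusion.** The conflict stands in limited form. For a subject with liver metastases who begins at Grade 2 AST/ALT and then has a drug-related event, the Grade 2 line, the Grade 3-4 line and footnote a do not give one consistent instruction. The Grade 2 line's restart condition lies below the entry grade. These are stated rules that disagree, not missing detail.

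The absence of a baseline alternative on the Grade 2 line and the placing of the footnote mark can be read directly from Table 3. The numerical examples rest on the assumed grade limits. Moving the Grade 3 boundary from 4.5 to 6×ULN shifts the baseline above which the inversion is possible from 3.0 to 4.0×ULN, still inside the entry limit.

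The number of such subjects is not given. It is probably small, since inclusion criterion 3 also requires LDH at or below the local ULN, and it may be zero. For scale only, one subject is 1/35 = 2.9% of planned enrolment and 1/28 = 3.6% of the main analysis population. No material effect on the response rate is shown. A reader might take discontinuation for toxicity to be a primary safety result. Section 8.2.3.2 does not list it: the primary safety endpoints are graded adverse events. Reasons for discontinuation are displayed under Section 8.2.5.3.

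**What to change.** Reconcile Table 1, the Grade 2 and Grade 3-4 AST/ALT lines of Table 3, footnote a, and the hepatic text in Section 5.6.1, so that subjects admitted at Grade 2 AST/ALT fall under one consistent hold, restart and discontinuation rule. State which lines and which columns footnote a modifies, including whether it changes the hold column and the last column of the Grade 3-4 line. Check that the separate guidance on events of clinical interest says the same. The choice of rule belongs to the sponsor's clinical and safety team; this review does not propose one.

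The cost is protocol wording and notice to sites. No new tests are needed, because AST and ALT are already in the scheduled chemistry panel (Table 5).
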